11.4 Analysis of Secondary Endpoints based on Adverse Events

The analysis for the primary endpoints described in [Section 11.3](#) will be repeated for the nC1-INH subjects, without the exclusion of TEAEs clearly identified to be related to an HAE therapy other than CSL312 and excluding the tables and listings associated with COVID-19.

The following summary tables will be provided for all subjects (C1-INH and nC1-INH) in the Safety Analysis Set, without excluding TEAEs clearly identified to be related to a HAE therapy other than CSL312:

- Overview table of TEAEs (same items as described in [Section 11.3](#)).
- Overview table of SAEs (same as above, restricted to SAEs).
- SAEs by SOC and PT.
- TEAEs by severity, SOC and PT.
- Related TEAEs by SOC and PT.
- TEAEs leading to study discontinuation by SOC and PT.
- TEAEs by 3-month windows. Rates will still be based on the cumulative safety period. Assignment of TEAEs to 3-month windows will be based on the start date of the AE, similarly as for HAE attacks (see [Section 10.2.1](#)). Unclear assignments due to incomplete AE start dates will be discussed during the PARM.
- AESI by SOC and PT as identified via SMQ (definition of AESI as in [Section 11.2](#)).
- Non-serious TEAEs by SOC and PT.
- Laboratory Findings reported as AEs.
- Anti-CSL312 antibodies.

Summary tables will be presented for the following:

- All subjects in the Safety Analysis Set (all subjects on 200 mg CSL312 once monthly, independent of the use of CSL312 200 mg AI or CSL312 200 mg NSD).
- Subjects on 200 mg CSL312 using AI.
- Subjects on 200 mg CSL312 using NSD.

TEAEs will be summarized by the number of subjects and percentage of subjects experiencing at least 1 TEAE, the number of events, as well as the event rates per injection and per subject year calculated in the same manner as for the primary endpoint described in [Section 11.3](#).

The following listings will be provided:

- Non TEAEs.
- TEAEs.
- TEAEs for Japanese subjects.
- TEAEs for adolescents.
- SAEs.
- SAEs with fatal outcome.
- AEs leading to study withdrawal.
- AEs leading to permanent discontinuation of study treatment.
- AESIs.
- Related AEs.
- TEAEs related to laboratory findings.
- AEs related to COVID-19.

TEAEs clearly identified to be related to an HAE therapy other than CSL312 will be flagged in listings.

Listings of AEs will at least include site, subject ID, HAE type, start and end date/times, reported term, SOC, PT, relationship to study drug, severity, whether it is serious, action taken. As stated in [Section 8.2.6](#) the listings will also include the most recent dose of CSL312 (dose level, device [NSD or AI] and date).

11.5 Clinical Laboratory Evaluations

The laboratory tests in Section 8.1.1 of the protocol will be summarized as described in this section. Unscheduled visits will be handled as described in [Section 8.2.5](#). Definition of the baseline assessment is in [Section 8.2.3](#).

The test names and units from the central laboratory transfer will be used. The sequence and groupings in which parameters are provided will match Table 2 of the protocol.

Separate summary tables for hematology, biochemistry, coagulation, urinalysis, and immunogenicity tests will be produced.

Summaries to be produced are:

- Laboratory values and changes from baseline by scheduled study visit for continuous tests and number and percentages per category for categorical tests.
- The number and percentage of subjects with clinically significant laboratory findings reported as AEs by test and visit. Those will be identified through the eCRF form ‘Clinical Significant Safety Lab Data.’.

The percentages for categorical tests will be based on the number of subjects with non-missing values at each visit.

The presence of anti-CSL312 antibodies will be summarized descriptively by visit. This summary will include the number and percentage of subjects who experience anti-drug antibodies.

A laboratory value that is outside the reference range is either high abnormal (value above the upper limit of the normal [ULN] reference range) or low abnormal (value below the lower limit of the normal [LLN] reference range). An abnormal laboratory value is not necessarily of potential clinical interest.

Listings of laboratory data will include test name and unit along with normal range, the sampling date and time, the test result, an assessment whether the result is high (above normal range) or low (below normal range). Any comments to the laboratory test will be provided in a separate listing, if applicable.

A by-subject listing for laboratory abnormalities will be provided in the same format as the laboratory listings described above but only containing information about abnormal laboratory results and including the laboratory category.

Listings to be produced are:

- All laboratory values including flags for values outside the normal range.
- Laboratory data for subjects with values outside the normal range.

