- D: CSL312-naïve subjects must complete at least 1 month of the Run-in Period and may enter the Treatment Period once they experience at least an average of 1 HAE attack per month during the Run-in Period (ie, at least 2 HAE attacks in total), and do not have laboratory clinical abnormalities assessed as clinically significant by the investigator in results of hematology, chemistry, or urinalysis assessments performed during Screening (see [Section 4.1.1.2](#)). For CSL312-naïve subjects, C1-INH functional activity and antigen, and C4 antigen concentration levels should be confirmed before entry into the Treatment Period. Eligibility to be confirmed before entry into the Treatment Period and any study assessments are performed.
- E: A physical examination will be conducted per the investigator's standard procedure, and will also include assessment of unilateral pain and / or swelling of the lower extremities for the purpose of screening for deep vein thrombosis.
- F: Height is collected at Day 1 only.
- G: Investigator completes IGART in Rave. Subjects complete SGART.
- H: Subjects rolling over from Study CSL312_3001 who have completed the AE-QoL and WPAI:GH as part of the last visit of Study CSL312_3001 will only need to complete the TSQM II at Day 1.
- I: Blood draws should be completed before study drug administration on the same day.
- J: Blood samples for potential future assessment of HAE biomarkers will be obtained during the Treatment Period. These samples will be stored for potential testing of HAE biomarkers and will be destroyed within 5 years after completion of the study or used for future research on HAE. These samples will not be collected in adolescents.

- K: The urine test for beta-human chorionic gonadotropin will be performed for women of childbearing potential only. A serum pregnancy test will be performed by the site if urine result is inconclusive. Female subjects of childbearing potential will perform home urine testing on months for which there is no onsite visit.
- L: The eDiary will be collected and deactivated for all subjects. For subjects who terminate the study early, the eDiary should be deactivated and collected either on date of early termination or at the Follow-up Visit as applicable. If the Follow-up Visit is conducted remotely, the device should be returned to the site.

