- G: PRO QoL assessments will be completed for the last time at the visit that the subject consents to Amendment 1 (ie, Month 12, Month 18, Month 24, or Month 30). If consent into Amendment 1 and switching to CSL312 200 mg AI is performed at an unscheduled visit after the Month 12 Visit, the last data for PRO QoL assessments will be from the last visit prior to the unscheduled visit (under the original protocol).
- H: Urine collection for urinalysis will be collected for the last time at the visit that the subject consents to Amendment 1 (ie, Month 12, Month 18, Month 24, or Month 30). If consent into Amendment 1 and switching to CSL312 200 mg AI is performed at an unscheduled visit after the Month 12 Visit, the last data for urinalysis will be from the last visit prior to the unscheduled visit (under the original protocol).
- I: On a visit day, blood draws should be completed on the same day of CSL312 administration.
- J: Per Amendment 1, collection of blood sample for hematology / biochemistry / coagulation analysis will be required every 12 months starting from the Month 12 Visit.
- K: Blood samples for potential future assessment of HAE biomarkers will be obtained for the last time at the visit that the subject consents to Amendment 1 (ie, Month 12, Month 18, Month 24, or Month 30). If consent into Amendment 1 and switching to CSL312 200 mg AI is performed at an unscheduled visit after the Month 12 Visit, the last collection of HAE biomarkers will be from the last visit prior to the unscheduled visit (under the original protocol). These samples will be stored for potential future assessment of HAE biomarkers and will be destroyed within 5 years after completion of the study. These samples will not be collected in adolescents.
- L: The urine test for beta-human chorionic gonadotropin will be performed only for women of childbearing potential. A serum pregnancy test will be performed by the site if urine result is inconclusive. Female subjects of childbearing potential will perform home urine testing on months for which there is no onsite visit.
- M: At the Follow-up Visit (conducted via telephone call), HAE attacks will be reported verbally, as the eDiary is deactivated at the End of Treatment Visit.

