2.2.2 Secondary Endpoints

Secondary Objective	Endpoint	Summary Measure(s)
Efficacy Endpoints		
1	Time-normalized number of HAE attacks	The time-normalized number (per month and year) of HAE attacks for the run-in and Treatment period.
1	The reduction in the attack rate during the Treatment Period compared to the Run-in Period	The percentage reduction and the number of subjects experiencing at least $\geq 50\%$, $\geq 70\%$, $\geq 90\%$ or equal to 100% (attack free) reduction in the time-normalized number of HAE attacks on Treatment compared to Run-in Period.
1	The time-normalized number of HAE attacks requiring on-demand treatment	The time-normalized number (per month and year) of HAE attacks requiring on-demand treatment in subjects on treatment.
1	The time-normalized number of moderate and / or severe HAE attacks	The time-normalized number (per month and year) of moderate and / or severe HAE attacks in subjects on treatment.
1	SGART	Number and percentage of subjects rating their response to therapy as good or excellent.

Secondary Objective	Endpoint	Summary Measure(s)
Safety Endpoints		
2	
 • SAEs • Deaths • Related TEAEs • TEAEs leading to study discontinuation • TEAEs by severity • Anti-CSL312 antibodies • Laboratory findings reported as an AE • AESIs (ie, thromboembolic events, abnormal bleeding events, severe hypersensitivity, including anaphylaxis events) • TEAE (for nC1-INH subjects only) 	The number and percentage of subjects experiencing the specified safety events on treatment with CSL312.

AE = adverse event; AESI = adverse event of special interest; nC1-INH = normal C1-esterase inhibitor; SAE = serious adverse event; SGART = Subject's Global Assessment of Response to Therapy; TEAE = treatment-emergent adverse event.

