8.6.3 Treatment Period (All CSL312_3001 Subjects and CSL312-naïve Subjects) for Original Protocol

8.6.3.1 Treatment Period Visit Day 1

CSL312-naïve subjects must complete all screening assessments, fulfill the eligibility criteria (ie, eligible subjects), and meet the Treatment Period entry criteria ([Section 4.1.1.2](#)).

For subjects who completed Study CSL312_3001 and choose to participate in Study CSL312_3002 (CSL312_3001 rollover subjects), assessments from Day 182 of Study CSL312_3001 will be used to fulfill assessments for Day 1 of Study CSL312_3002

(ie, the last study visit of CSL312_3001 and the first study visit of Treatment Period in CSL312_3002 occur on the same day).

If a subject did not participate in a Screening Visit (CSL312_3001 subjects), then a written informed consent / assent must be obtained before any study-specific assessments or procedures are performed at the first visit in the Treatment Period.

The following procedures / assessments will be conducted and documented:

- Written informed consent for subjects rolling over from Study CSL312_3001.
- Confirm eligibility for Treatment Period
- Perform physical examination.
- Record vital signs, including body weight and height.
- TSQM II (subjects ≥ 18 years).
- AE-QoL (subjects ≥ 18 years).
- WPAI:GH (subjects ≥ 16 years).

Note: Subjects rolling over from Study CSL312_3001 who have completed the AE-QoL and WPAI:GH as part of the last visit of Study CSL312_3001 will only need to complete the TSQM II at Day 1.

- Urine collection for urinalysis.
- Collection of blood to assess:
 - Hematology.
 - Biochemistry.
 - Coagulation.
 - Retention sample for HAE biomarkers (adults only).
 - PK / PD.
 - Immunogenicity.
- Collect urine for pregnancy test (for women of childbearing potential).
- PRO / eCOA tablet training

- Review eDiary instructions with subject
- Review eDiary data and assess / document HAE attacks.
- Confirm access to on-demand HAE medication.
- IRT CSL312 kit assignment.
- Accountability of CSL312

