8.2.3 Baseline Definition

Baseline is defined as the most recent, non-missing value prior to first study drug administration in this study. Determination of the baseline value considers unscheduled visits during the Run-in and Screening Periods.

If the measurement of a variable is not made on a given subject prior to first study drug administration, the baseline value for that subject will be set to missing for that variable.

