8.4 Study Periods Relative to Treatment

AEs, HAE attacks, laboratory data, vital signs and other measurements will be assigned to the study time periods defined below.

Table 3 Definitions of Study Periods Relative to Treatment

Period	Start Date	End Date
Screening Period	Date of Informed Consent	Run-in Period Start Date
Run-in Period	Run-in Period Start Date	Day 1 Visit date of the Treatment Period or Date of Run-in Non-completion [whichever is first]
Treatment/Efficacy evaluation period	Date of Day 1 Visit of Treatment Period	Date of EOT Visit or EOS date [whichever is first]
Treatment/Efficacy before transition to AI evaluation period	Date of Day 1 Visit of Treatment Period	Date of first dose with AI – 1 Day (see Section 8.2.1)
Treatment/Efficacy after transition to AI evaluation period	Date of first dose with AI (see Section 8.2.1)	Date of EOT Visit or EOS date [whichever is first]
Follow-up	Date of EOT Visit	Date of Final/ Follow-up Visit
Safety evaluation period	Date and start time of First CSL312 Administration as entered in the eDiary	Date of Final/ Follow-up Visit
Safety Evaluation before transition to AI evaluation period	Date and start time of First CSL312 Administration as entered in the eDiary	Date of first dose with AI – 1 Day (see Section 8.2.1)
Safety Evaluation after transition to AI evaluation period	Date of first dose with AI (see Section 8.2.1)	Date of Final/ Follow-up Visit

The EOS date is the date entered in the Conclusion of Subject Participation eCRF page and should generally be identical to the date of the Follow-up Visit.

The handling of any unplanned dose changes or device changes will be discussed in the PARM. The safety evaluation period consists of the Treatment/Efficacy evaluation period plus the Follow-up Period.

Screening and Run-in periods will not be performed for roll-over subjects, instead relevant endpoint data (such as HAE attacks during the Run-in period) will be used from the CSL312_2001 and CSL312_3001 studies.

The duration of the Efficacy evaluation and the Safety evaluation period in days will be calculated as:

End Date – Start Date + 1 Day.

Screening, Run-in and Follow-up periods in days will be calculated as:

End Date – Start Date.

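### The anti-CSL312 antibody count does not require a prior negative sample and has no device attribution rule, so antibodies carried over from a lead-in study or from the NSD can be reported as on-study or autoinjector findings

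*SAP*

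**What the plan says.** Protocol 2.2.2 lists anti-CSL312 antibodies among the secondary safety endpoints, with this summary measure: "The number and percentage of subjects experiencing the specified safety events on treatment with CSL312". Protocol 1.4 names immunogenicity as a potential risk and says that antibody development will be monitored.

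SAP 11.5 gives the analysis in two sentences: "The presence of anti-CSL312 antibodies will be summarized descriptively by visit", and "This summary will include the number and percentage of subjects who experience anti-drug antibodies". The verb *experience* is not defined. SAP 8.2.3 has a general baseline rule ("Baseline is defined as the most recent, non-missing value prior to first study drug administration in this study"), but SAP 11.5 uses baseline only for changes in continuous tests. Categorical tests get counts per category.

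SAP 11.4 includes the antibody table among those shown overall, for AI users and for NSD users. SAP 8.4 states that "AEs, HAE attacks, laboratory data, vital signs and other measurements will be assigned to the study time periods defined below". In its Table 3, the safety period before the AI ends the day before the first AI dose, and the AI period starts on the date of that dose.

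For rollovers, the Day 1 sample comes from the last lead-in visit. For CSL312_3001, "assessments from Day 182 of Study CSL312_3001 will be used to fulfill assessments for Day 1 of Study CSL312_3002" (Protocol 8.6.3.1). For CSL312_2001 it is the Week 57 visit (Protocol 8.6.4.1).

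**The concern.** An immunogenicity endpoint is meant to show how many subjects develop antibodies on the product. That needs a prior status for each subject. The SAP supplies one for its other event endpoints: adverse events are split at the first dose and again at the AI reference date and time (SAP 11.2), and attacks are split at the first dose (SAP 10.2.1). Antibodies have no such split.

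Two kinds of record are then counted in the wrong place. A rollover may have formed antibodies in the lead-in study and still be positive at Month 6 or Month 12 here. An AI user may have formed antibodies on the NSD, since switching starts no earlier than Month 12, and still be positive at a later sample. The first inflates the on-study percentage. The second puts NSD antibodies in the AI column, which a reader will take as the study's immunogenicity result for the new device.

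**Working it through.** There is no antibody rate in either document, so there is no stated figure to reproduce. The check is of definitions, followed by an illustration.

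**1. Is prior status used anywhere?** SAP 11.5 speaks of presence and of an undefined *experience*. No baseline-negative, treatment-emergent or boosted class is given. The by-visit table shows prevalence at each visit, but not whether a subject positive at Month 12 was negative before.

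**2. Is there a device rule?** SAP 7.1 splits by the device in use when the event started, but for adverse event tables only. An antibody has no recorded start. A persisting NSD antibody is therefore present in any AI-period sample, whenever the subject switched.

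**3. The switch-day sample.** Under Amendment 1, immunogenicity is drawn at Months 12, 24 and 36 and at End of Treatment. The scheduled switch visits are Months 12, 18, 24 and 30, and an unscheduled switch visit has no other assessments. The positions are:

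| Switch at | Antibody sample that day | Placed by Table 3 in |
|---|---|---|
| Month 12 or 24 | Yes | AI period |
| Month 18 or 30 | No | not applicable |
| Unscheduled visit | No | not applicable |

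So 2 of the 4 scheduled switch visits carry a sample, and Table 3's date rule puts it under the AI even if drawn before the first AI dose. The Amendment 1 schedule does not fix the order ("On a visit day, blood draws should be completed on the same day of CSL312 administration"), whereas the schedules under the original protocol did ("Blood draws should be completed before study drug administration on the same day"). In either order, a sample taken that day reflects status before the AI could have had any effect.

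**4. How many rollovers could there be?** Protocol 1.2.3.2 reports 36 completers in CSL312_2001 and 64 randomised in CSL312_3001, some to placebo. The upper bound is 36 + 64 = 100. Against about 150 planned (SAP 4.4), 100/150 = 67%. The number with lead-in exposure is lower, because CSL312_3001 placebo subjects are included.

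**5. Overall column, illustration.** Let N = 150, R = 100, b = assumed share of rollovers positive at entry and still positive at an on-treatment sample, t = assumed treatment-emergent rate among the rest.

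Percentage counted = [bR + t(N − bR)] / N

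| b | t = 1% | t = 3% |
|---|---|---|
| 0% | 1.5/150 = 1.0% | 4.5/150 = 3.0% |
| 1% | (1 + 1.49)/150 = 1.7% | (1 + 4.47)/150 = 3.6% |
| 2% | (2 + 1.48)/150 = 2.3% | (2 + 4.44)/150 = 4.3% |
| 5% | (5 + 1.45)/150 = 4.3% | (5 + 4.35)/150 = 6.2% |

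A treatment-emergent count, with N − bR as denominator, stays at 1.0% or 3.0% in every row.

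**6. AI column.** With k carried-over subjects and an assumed 100 to 150 AI users, the contribution is k/150 to k/100. For k = 1 this is 0.7% to 1.0%; for k = 3, 2.0% to 3.0%; for k = 5, 3.3% to 5.0%.

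**The case against.** The strongest reply is that the SAP never says every positive sample counts. *Experience* is undefined, the summary is by nominal visit, so Day 1 status is visible, and all laboratory values are listed with dates. That stands as far as the wording goes. It does not answer the point, because prevalence by visit cannot separate new from persisting antibodies, and the number and percentage of subjects still need a rule.

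A reader might infer that a subject positive only on the pre-dose Day 1 sample is counted as a case. The documents do not support that. The endpoint is limited to time on treatment, and Table 3 starts the safety period at the time of the first dose. SAP 8.4 assigns a pre-dose Day 1 event to Run-in for CSL312-naïve subjects and to no period for rollovers. That rule is written for events, so its reach to laboratory samples is not certain, but nothing points the other way.

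A reader might also infer that every AI switch brings a switch-day sample into the AI column. That is true only at Months 12 and 24. SAP 8.2.1 also defines an AI reference date and time, so the SAP is not date-only throughout, although Table 3 is.

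Nor can this be called the only immunogenicity evidence for the autoinjector. CSL312_1004 also gives CSL312 by AI (Protocol 1.2.3.1), and the documents do not say whether antibodies are measured there. The AI holds the same prefilled syringe as the NSD, and no hypothesis test rests on this endpoint. Both lower the stakes.

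**Conclusion.** The concern holds in this form: the subject-level antibody count is not defined as treatment-emergent, and the AI and NSD columns have no antibody attribution rule. Persisting lead-in antibodies are counted as on-study findings, and persisting NSD antibodies as AI findings.

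The size cannot be fixed from the documents. Each carried-over subject adds about 0.7 to 1.0 percentage point to the AI column, assuming 150 to 100 AI users. For the overall column, an assumed 2% to 5% of rollovers positive at entry would turn a treatment-emergent rate of 1% into 2.3% to 4.3%. That rests on the upper bound of 100 rollovers and on every such antibody persisting to an on-treatment sample. A general claim that the endpoint is overstated by some fixed multiple would need an entry prevalence and a persistence rate, and the documents give neither.

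The matter should be settled before database lock. It affects how a descriptive safety result is read, not a formal conclusion.

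**What to change.** In SAP 11.5:

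- Define the number and percentage of subjects as a treatment-emergent count: a positive post-dose sample in a subject negative at the pre-dose Day 1 sample of this study. For rollovers, also report it against the pre-exposure lead-in sample where that result exists.
- Report Day 1 positives separately, and keep by-visit prevalence as a second table.
- In the AI column, count only subjects negative at the last sample up to and including the date of the first AI dose, with that group as denominator.
- Flag as not attributable to a device any positive whose last negative sample came before the switch visit. This arises with Month 18, Month 30 and unscheduled switches. For example, a subject switching at Month 18 is sampled at Months 12 and 24, so a first positive at Month 24 could have formed on either device.

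The cost is SAP wording and programming, with no new sampling. The SAP describes importing lead-in Run-in attacks and on-demand medication (SAP 9.4 and 10.2.1) but not antibody results, so the lead-in comparison needs one additional import, and it is not stated that a pre-exposure sample exists for every rollover. Denominators become smaller, and some AI-period positives will remain unassigned.
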